3.2 Study Population

All adult patients with arteriovenous access flow dysfunction in Hospital Kuala Lumpur and University Malaya Medical Centre during the period 1 July 2023 – 30 June 2024.

3.3 Inclusion Criteria

NO.	INCLUSION CRITERIA	EVALUATION METHOD.
1	Patient able to comprehend English or Malay language.	Speak to patient.
2	Patient aged ≥ 18 years and ≤ 80 years.	Examine patient personal data.
3	Patient is willing to comply with protocol.	Ask the patient.
4	Native AVF that is able to provide prescribed dialysis consistently with 2 needles for $>2/3$ of dialysis sessions within 4 consecutive weeks.	Ask the patient & examine dialysis record.
5	Patient has a reasonable expectation of remaining on haemodialysis for 6 months.	Ask the patient.

6	Dampened thrill or pulsatile flow.	Palpate the arteriovenous fistula.
7	Volume flow (VF) <500 ml/min.	Ultrasound doppler measurement.
8	Severe stenosis (>50%) of arteriovenous (AV) access measured on color image and confirmed by peak systolic velocity (PSV) ratio of ≥ 3 in the inflow artery, anastomosis, or in the outflow vein.	Ultrasound doppler measurement.

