Arteriovenous fistulas (AVF) are the vascular access of choice for hemodialysis patients. In the United States from August 2010 to August 2013, arteriovenous fistula (AVF) use increased from 63% to 68% and across 20 other countries in 2013, arteriovenous fistula (AVF) use ranged from 49% to 92%.¹ Patency and functionality of haemodialysis access influences survival and quality of life for patients with chronic renal failure. Progressive narrowing of the perianastomotic lumen or a more proximal part of venous circulation as a result of intimal proliferation is the main cause of failure of arteriovenous fistula. The use of Doppler sonography allows identification of more than 50% arteriovenous fistula stenosis, with 92% sensitivity and 84% specificity.² Percutaneous transluminal fistuloplasty is a well-established therapeutic option for patients with haemodialysis vascular access stenosis. It is conventionally guided and monitored radiographically, but this carries the risks of ionizing radiation exposure and of adverse reaction to contrast media and this is the usual practice in Hospital Kuala Lumpur and University Malay Medical Centre.

Recently, we have observed an increasing role of ultrasonography (USG) in imaging of arteriovenous fistula. Superficial location of arteriovenous fistula allows for simple and reliable visualization of vessels, guidewire, catheter, balloon, etc., with significant technical advantages including the ability to directly visualize puncture sites, stenosis, thrombus, spasm, and extravascular flow in real time. Recent studies showed that percutaneous transluminal fistuloplasty can be performed under only sonographic guidance without using a fluoroscopic machine and it is as effective as conventional percutaneous transluminal fistuloplasty as shown in Appendix 1. Since more than a decade of described ultrasound-guided fistuloplasty, many small series have been published till date, but most of them studied small number population and without direct head-to-head comparison with fluoroscopy-guided fistuloplasty as shown in Appendix 2. To overcome these limitations and further evaluate the efficacy of the procedure, we would like to compare patency of arteriovenous access flow dysfunction post ultrasound-guided fistuloplasty versus fluoroscopy-guided fistuloplasty.

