We would like to research upon the efficacy of ultrasound-guided fistuloplasty as an alternative to fluoroscopy-guided fistuloplasty to prolong patency of patients with arteriovenous access flow dysfunction.

2. Objective

To determine the efficacy of ultrasound-guided fistuloplasty compared to fluoroscopy-guided fistuloplasty in patients with arteriovenous access flow dysfunction.

3. Methodology

Study design: Multicentre, randomized controlled trial.

Location: Hospital Kuala Lumpur and University Malaya Medical Centre.

Population: Vascular clinic patients in Kuala Lumpur Hospital and University Malaya Medical Centre.

1. Treatment group: Patients who underwent ultrasound-guided fistuloplasty for arteriovenous access flow dysfunction are assessed prospectively for a period of 6 months.
2. Control group: Patients who underwent fluoroscopy-guided fistuloplasty for arteriovenous access flow dysfunction are assessed prospectively for a period of 6 months.

Sampling method: Simple random sampling.

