Fluoroscopy is used in the control group to assess for technical success. On table fistulogram visualization of less than 30% recoil of the target lesion signifies technical success. After a satisfactory result, a figure of 8 suture is placed with manual inflow occlusion. Post procedure, patients will be observed for any signs of haematoma or bleeding. If there are no immediate complications, patients will be discharged on the same day.

These procedures will be performed either by vascular surgeons or interventional radiologists below tabled:

OPERATOR	FISTULOPLASTY		CENTRE	DESIGNATION
	ULTRASOUND-GUIDED	FLUOROSCOPY-GUIDED		
[name] [name]	✓		University Malaya Medical Centre	Vascular surgeon
TBD		✓	University Malaya Medical Centre	Interventional radiologist
[name] [name]	✓	✓	Hospital Kuala Lumpur	Vascular surgeon

Cases with serious complications such as extravascular leak or significant pseudoaneurysm will be admitted for monitoring. If the complications are resolved then, the patient will be discharged. Follow-up may be scheduled earlier.

Follow-up will be done at two weeks, one month, three months and six months.

Assessment during follow-up includes:

- Resolution of symptoms (prolonged post dialysis bleeding or difficult access cannulation).
- Reduction of venous dialysis pressure to below predefined threshold values. (the acceptable value is less than 150mmHg)
- Measurement of the volume flow (the acceptable value is more than 500ml/min), flow characteristics (the acceptable characteristic is laminar flow) and diameter of the target lesion (the acceptable diameter is between 5-6mm) using duplex ultrasound.

[figure not shown]
In the event of a negative outcome during the first post fistuloplasty follow-up, it will be determined whether it is due to:

- a missed stenotic segment invisible to ultrasound or
- it is a case of severe stenotic segment refractory to fistuloplasty.

Patients belonging to the former category will cross-over to the fluoroscopic-guided fistuloplasty group. In the latter case, there is no reason to repeat the fistuloplasty regardless of the imaging method (ultrasound or fluoroscopy). Ideally, these particular patients should receive drug-coated balloon (DCB) fistuloplasty which is beyond the scope of this study. There is no alternative apart from switching to fluoroscopic-guided fistuloplasty.

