3.4 Exclusion Criteria

NO.	EXCLUSION CRITERIA	EVALUATION METHOD.
1	Prior history of fistuloplasty.	Ask the patient and examine hospital record.
2	Thrombosed or completely occluded fistula or outflow vein.	Palpate the arteriovenous fistula and by using ultrasound doppler.
3	Non-mature AVF.	Palpate the arteriovenous fistula and by using ultrasound doppler.
4	Arteriovenous grafts.	Ask the patient, examine hospital record and by using ultrasound doppler.
5	Suspected central vein stenosis/ cephalic arch stenosis - arm edema or Doppler detected suspicion of the same.	Ultrasound doppler measurement
6	Non consenting patient.	Ask the patient
7	Metastatic cancer or terminal medical condition.	Ask the patient and examine hospital record.
8	Limited life expectancy (<6 months).	Ask the patient and examine hospital record.
9	Blood coagulation disorders (haemophilia/ Von Willebrand disease/ clotting factor deficiencies/ liver disease).	Ask the patient and examine hospital record.
10	Connective tissue disease (rheumatoid arthritis/ lupus).	Ask the patient and examine hospital record.
11	Sepsis or active infection.	Ask the patient and examine for any signs of infection.
12	Planned access abandonment within 6 months (eg, peritoneal dialysis or transplant).	Ask the patient.
13	Pregnant women or women of childbearing potential who are not following an effective method of contraception.	Ask the patient and obtain urine pregnancy test.
14	Allergy or other known contraindication to iodinated media contrast.	Ask the patient and examine hospital record.
15	Patient enrolled in another access maintenance trial.	Ask the patient.

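### Entry is gated by duplex while the objective is unrestricted, and cross-over plus per-protocol analysis can take missed-segment failures out of the ultrasound arm

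*Combined protocol and SAP*

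**What the plan says.** **Entry.** Section 3.3, criterion 8, requires "Severe stenosis (>50%) of arteriovenous (AV) access measured on color image", with a peak systolic velocity ratio of at least 3 as confirmation, and criterion 7 requires "Volume flow (VF) <500 ml/min". Ultrasound Doppler is the evaluation method for both. No fistulogram or other non-ultrasound route to eligibility is given. Section 3.4, criterion 5, removes "Suspected central vein stenosis/ cephalic arch stenosis - arm edema or Doppler detected suspicion of the same". Other criteria there remove earlier fistuloplasty, occluded access and grafts.

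**Scope.** Section 3.2 gives the population as "All adult patients with arteriovenous access flow dysfunction in Hospital Kuala Lumpur and University Malaya Medical Centre", within the recruitment dates. Section 2 gives the objective as "To determine the efficacy of ultrasound-guided fistuloplasty compared to fluoroscopy-guided fistuloplasty in patients with arteriovenous access flow dysfunction". Neither mentions duplex visibility, lesion site or first treatment.

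**After randomisation.** If the first follow-up is negative, Section 3.1 asks which of two causes applies. The first is "a missed stenotic segment invisible to ultrasound or"; the second is a severe stenosis refractory to dilation. Patients in the first category cross over to the fluoroscopy group. Follow-up starts at two weeks, and the primary outcome is patency at one, three and six months.

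**Analysis.** Section 3.9 specifies a per-protocol analysis. It does not define who belongs to that set, in which arm a crossed-over patient is counted, or whether cross-over ends patency.

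**The concern.** The entry test is one of the two imaging methods under comparison, so the sample is selected towards lesions that ultrasound can show. A result from that sample does not extend to patients whose only lesion is hidden from duplex, or to those with suspected central or arch disease, but the objective and population statement do not say so.

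The second problem affects the estimate itself. A segment that ultrasound misses is the one failure the protocol names as specific to ultrasound guidance. Patients with that failure are the ones moved to fluoroscopy. A per-protocol analysis would commonly leave out a patient who switched, or count that patient under the treatment received. Either way the failure leaves the ultrasound arm. The same kind of failure would then be thinned once at entry and again in the analysis. Only the second filter acts on one randomised arm, so only the second can bias the comparison.

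**Working it through.** **1. The plan's own figure.** Inputs from Section 3.6: 90% and 52.4%, alpha 0.05, power 80%. With the two-sided pooled-variance formula, mean rate (0.90 + 0.524)/2 = 0.712:

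n = [1.96 × √(2 × 0.712 × 0.288) + 0.842 × √(0.90 × 0.10 + 0.524 × 0.476)]² / 0.376² = 21.6, so 22 per group.

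This matches the plan, and 22 × 1.2 = 26.4 gives the stated 27. The sample size is not in dispute here.

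**2. Entry against scope.** Criteria 7 and 8 and exclusion 5 apply to everyone before allocation, so they cannot unbalance the arms. They do define a narrower group than Sections 2 and 3.2 describe.

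**3. Timing.** By the schedule the first follow-up is at two weeks. A cross-over decided there comes before all three primary time points, so a crossed-over patient could be patent at one, three and six months because of fluoroscopy.

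**4. What the handling rule does.** The documents give no cross-over rate, so k = 1 to 3 missed-segment patients is an assumption. Further assumptions: 27 per arm, dropout ignored, the other 27 − k ultrasound patients 90% patent, and control 52.4% patent (0.524 × 27 = 14.15).

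- A, kept in the allocated arm and counted as failures: 0.9(27 − k)/27 against 52.4%.
- B, removed: 90% against 52.4%.
- C, moved to fluoroscopy and patent there: 90% against (14.15 + k)/(27 + k).
- D, moved to fluoroscopy and not patent there: 90% against 14.15/(27 + k).
- E, kept in the allocated arm, but patency after fluoroscopy credited to ultrasound: [0.9(27 − k) + k]/27 against 52.4%.

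Difference, ultrasound minus fluoroscopy, in percentage points:

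| Handling | k = 1 | k = 2 | k = 3 |
|---|---|---|---|
| A | 34.3 | 30.9 | 27.6 |
| B | 37.6 | 37.6 | 37.6 |
| C | 35.9 | 34.3 | 32.8 |
| D | 39.5 | 41.2 | 42.8 |
| E | 38.0 | 38.3 | 38.7 |

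Here every alternative to A favours ultrasound. Against A, removal (B) adds 3.3, 6.7 and 10.0 points. Row E shows that keeping patients in their allocated arm is not enough unless the cross-over is also counted as a failure.

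**The case against.** A broad source population followed by restrictive criteria is normal protocol structure. The criteria are openly listed directly after Section 3.2, and ultrasound-guided dilation needs a lesion that ultrasound can show, so this may be the intended population. The word *all* appears only in the population statement; the objective is merely unqualified. Section 1 speaks of ultrasound as an alternative and nowhere says that fluoroscopy can be abandoned. All of this stands, and it is why the scope point is one of wording and applicability.

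It can also be said that no sentence removes crossed-over patients. That is true, but per-protocol analysis is specified, the set is undefined, and Section 3.1 sends these patients to the other group. Following the plan as written permits removal or reassignment, and nothing prevents it.

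A reader might infer more than the documents support:

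- **That ultrasound is tested only where it can see.** Criterion 8 requires one visible lesion and does not exclude further hidden ones. Section 3.1 expects some among enrolled patients. Exclusion 5 removes only suspected central or arch disease, partly through arm oedema.
- **That only the control arm's fistulogram can reveal a hidden lesion.** Section 3.1 looks for a missed segment after a negative first follow-up in ultrasound patients.
- **That control patients will be dropped after a fistulogram finding.** No section says so.
- **That the cited Doppler accuracy ("with 92% sensitivity and 84% specificity") gives the size.** One minus 92% is 8%, a miss rate among stenoses. It is not the prevalence of a second hidden lesion in patients who already have a visible one. Nor is 92% the sensitivity of the entry rule, which also needs the velocity ratio and low flow.
- **That control-arm fistulograms could measure what duplex misses.** Section 3.1 describes them for recoil of the target lesion and does not say how much of the circuit is imaged.

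**Conclusion.** The point holds in two parts. First, the objective and population statement are wider than the sample. This limits applicability and leaves the randomised comparison, the sample size and alpha untouched. Second, cross-over from the ultrasound arm combined with an undefined per-protocol analysis can remove or reassign the failures specific to ultrasound, and that would favour ultrasound. The size cannot be taken from the documents because they give no cross-over frequency. If 1 to 3 of 27 ultrasound patients were affected, at the planned rates, removal would overstate the difference by 3.3 to 10.0 points. The direction under reassignment (rows C and D) rests on those rates; the amount depends on whether the repeat procedure holds. The second part matters more and should be settled before any outcome data are analysed.

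**What to change.** 1. **Section 3.9.** State that a lesion first found after randomisation, by fistulogram or at cross-over in either arm, never removes or reassigns a patient. Every patient is analysed in the allocated arm. Cross-over for a missed segment counts as loss of patency in the ultrasound arm at that visit and all later ones. To keep the rule even-handed, a repeat procedure for a missed lesion in the fluoroscopy arm should count in the same way.
2. **Sections 2 and 3.2, the synopsis and the reported conclusion.** Limit the wording to first fistuloplasty of a duplex-identified stenosis in a native fistula without suspected central or cephalic arch disease.

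No change to eligibility, treatment, visits or sample size is needed. The cost is a few sentences, a narrower claim and possibly a less favourable ultrasound result. A control-arm estimate of lesions missed by duplex should not be added unless the extent of the fistulogram is first shown to support it.

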3.4 Exclusion Criteria

NO.	EXCLUSION CRITERIA	EVALUATION METHOD.
1	Prior history of fistuloplasty.	Ask the patient and examine hospital record.
2	Thrombosed or completely occluded fistula or outflow vein.	Palpate the arteriovenous fistula and by using ultrasound doppler.
3	Non-mature AVF.	Palpate the arteriovenous fistula and by using ultrasound doppler.
4	Arteriovenous grafts.	Ask the patient, examine hospital record and by using ultrasound doppler.
5	Suspected central vein stenosis/ cephalic arch stenosis - arm edema or Doppler detected suspicion of the same.	Ultrasound doppler measurement
6	Non consenting patient.	Ask the patient
7	Metastatic cancer or terminal medical condition.	Ask the patient and examine hospital record.
8	Limited life expectancy (<6 months).	Ask the patient and examine hospital record.
9	Blood coagulation disorders (haemophilia/ Von Willebrand disease/ clotting factor deficiencies/ liver disease).	Ask the patient and examine hospital record.
10	Connective tissue disease (rheumatoid arthritis/ lupus).	Ask the patient and examine hospital record.
11	Sepsis or active infection.	Ask the patient and examine for any signs of infection.
12	Planned access abandonment within 6 months (eg, peritoneal dialysis or transplant).	Ask the patient.
13	Pregnant women or women of childbearing potential who are not following an effective method of contraception.	Ask the patient and obtain urine pregnancy test.
14	Allergy or other known contraindication to iodinated media contrast.	Ask the patient and examine hospital record.
15	Patient enrolled in another access maintenance trial.	Ask the patient.

3.5 Withdrawal Criteria

Subjects can choose to withdraw at any time. Subjects may be withdrawn if the investigator deems that it is detrimental or risky for the subject to continue. All withdrawn subjects should attend the final study visit. Withdrawn subjects will not be replaced.

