3.1 Study Type and Design

This is an experimental study employing a prospective randomized controlled trial.

The primary outcome would be to compare the patency of arteriovenous fistula at one, three and six months.

Secondary outcomes shall include:

- To capture data regarding variables that may affect patency of arteriovenous access flow dysfunction post ultrasound-guided fistuloplasty versus fluoroscopy-guided fistuloplasty,
- To compare technical success (defined as clinical palpable thrill, radiographic finding of less than 30% recoil and ultrasonographic finding of continuous segment of dilated vein to 5-6mm and continuous flow rate of more than 500ml/min) in patients with arteriovenous access flow dysfunction receiving ultrasound-guided fistuloplasty versus fluoroscopy-guided fistuloplasty and
- To compare complication rates in patients with arteriovenous access flow dysfunction receiving ultrasound-guided fistuloplasty versus fluoroscopy-guided fistuloplasty

Patients are randomized using simple randomization method. Treatment plans are divided equally between ultrasound-guided fistuloplasty and fluoroscopy-guided fistuloplasty. An application “sealedenvelope.com” is used for this purpose. The application does this via a built in random number generator.

After assessing for eligibility, patients will be randomized equally with a ratio 1:1 to ultrasound-guided fistuloplasty group and fluoroscopy-guided fistuloplasty group.

Both interventions will be done in operation theatre to maintain sterility. After cleaning and draping the area of interest, local anaesthesia is given to the puncture site. A puncture needle is used to gain access to the arteriovenous fistula followed by a guide wire. Then, a sheath with an appropriate size is placed and a balloon catheter of adequate size is inserted over the guide wire and inflated for 2 minutes. Ultrasound is used in the subject group to monitor technical success. On table visualization of continuous segment of dilated vein to 5-6mm and continuous flow rate of more than 500ml/min signifies the end points of the procedure.

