3.6 Sample Size

Based on a power of 80% ($\beta=0.2$), alpha of 0.05, a response anticipated difference of 90% in ultrasound-guided fistuloplasty group and 52.4% in fluoroscopy-guided fistuloplasty group, the calculated sample size for each group is 22 patients. Allowing for 20% dropout, a final sample size of 27 per group will be used.

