3.7 Study Duration and Timeline

- Stage 1, data collection and data analysis - 8-12 months.
- Stage 2, follow-up - 6 months.
- Stage 3, presentation and publication - 6-12 months.

The participation duration for each subject is 6 months.

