3.8 Study Visits and Procedures

Follow-up will be done at two weeks, one month, three months and six months.

Assessment during follow-up includes:

- Resolution of symptoms (prolonged post dialysis bleeding or difficult access cannulation).
- Reduction of venous dialysis pressure to below predefined threshold values. (the acceptable value is less than 150mmHg)
- Measurement of the volume flow (the acceptable value is more than 500ml/min), flow characteristics (the acceptable characteristic is laminar flow) and diameter of the target lesion (the acceptable diameter is between 5-6mm) using duplex ultrasound.

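### Section 3.5 allows discretionary withdrawal after a one-off procedure and then asks only for an undefined final visit, so the one- and three-month patency readings can be lost

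*Combined protocol and SAP*

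**What the plan says.** Section 3.5 gives the investigator a discretionary power and limits what is asked for afterwards: "Subjects may be withdrawn if the investigator deems that it is detrimental or risky for the subject to continue. All withdrawn subjects should attend the". It sets no criteria beyond the investigator's judgement and does not separate stopping treatment from stopping follow-up. The second of these sentences reads in full "All withdrawn subjects should attend the final study visit", and a third one adds "Withdrawn subjects will not be replaced". The final visit is not defined.

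Section 3.1 sets the primary outcome at three time points: "The primary outcome would be to compare the patency of arteriovenous fistula at one, three and six months". Section 3.8 gives the schedule: "Follow-up will be done at two weeks, one month, three months and six months". Section 3.7 adds: "The participation duration for each subject is 6 months". The general objective in the synopsis table refers to patency at six months.

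Section 3.1 describes one balloon procedure, with same-day discharge if there is no immediate complication. Section 3.6 plans for loss: "Allowing for 20% dropout, a final sample size of 27 per group will be used". Section 3.9 specifies a per-protocol analysis and gives no rule for missing patency data. No section describes blinding of investigators or assessors, or asks for the reason for a withdrawal to be recorded.

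**The concern.** In a trial of continuing treatment, a rule of this kind protects the patient from further exposure. Here the randomised procedure is over on the day it is done. What remains is clinic visits for symptoms, venous pressure and duplex measurement, so an investigator who withdraws a patient for safety mostly ends observation. Section 3.5 then releases that patient from every visit except the last.

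The triggers for such a judgement could be related to outcome. Section 3.1 expects some negative results at the first follow-up, which is at two weeks and so comes before every primary time point. For refractory stenosis it describes further treatment as outside the study. It also names serious complications that need admission. If patients with these courses are withdrawn more often, and more often in one arm, the interim patency rates would come from a selected group. The allowance in section 3.6 protects power against random loss, but it does not protect against selective loss.

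**Working it through.** **1. Which primary readings survive withdrawal.** For a patient withdrawn after the two-week visit, taking 3.1, 3.5 and 3.8 together:

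| Primary time point | Requested after withdrawal? |
|---|---|
| One month | No |
| Three months | No |
| Six months | Yes, if the final visit is the six-month visit; not stated |

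So two of the three primary time points are not requested, and the third depends on an undefined term. Sections 3.7 and 3.8 (six months' participation, last scheduled visit at six months) favour the six-month meaning.

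**2. The plan's own sample size (3.6).** Inputs: 90% and 52.4%, alpha 0.05 (two-sided assumed, as sidedness is not stated), power 80%. With the pooled two-proportion formula and a mean rate of 0.712:

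n = [1.960 × √(2 × 0.712 × 0.288) + 0.842 × √(0.90 × 0.10 + 0.524 × 0.476)]² / 0.376² = 21.6, rounded up to 22. This matches the plan.

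For dropout, 22 × 1.2 = 26.4 gives the plan's 27 (22 / 0.8 = 27.5 would give 28). Power is 88.5% with 27 per arm and 80.9% with 22. Random loss at the planned rate is therefore covered, and what remains is selection.

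**3. Outer bound on six-month patency.** Assume 5 of 27 per arm (27 − 22) have no six-month status and the planning rates hold among the 22 seen. These are rates, not whole counts: 0.90 × 22 = 19.8 and 0.524 × 22 = 11.528.

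| Status of the 5 lost per arm | Ultrasound, all 27 | Fluoroscopy, all 27 | Gap (points) |
|---|---|---|---|
| Ultrasound all failed, fluoroscopy all patent | 19.8/27 = 73.3% | 16.528/27 = 61.2% | 12.1 |
| All failed in both arms | 73.3% | 11.528/27 = 42.7% | 30.6 |
| All patent in both arms | 24.8/27 = 91.9% | 61.2% | 30.6 |
| Ultrasound all patent, fluoroscopy all failed | 91.9% | 42.7% | 49.2 |

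The observed gap is 90 − 52.4 = 37.6 points. If those lost have the same status in both arms, the gap is 37.6 × 22/27 = 30.6 whichever status it is. With 2 lost per arm, the extremes are 22.5/27 − 15.1/27 = 27.4 and 24.5/27 − 13.1/27 = 42.2 points.

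By a pooled z test, the observed gap at 22 per arm gives p of about 0.006. Over all 27 it is about 0.02 if all those lost failed, and about 0.34 at the 12.1-point extreme.

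**4. The selection mechanism in one arm.** Take 21 of 27 patent (77.8%, close to the 77.6% six-month rate of one ultrasound series in Appendix 1). If 3 failures leave the analysis uncounted, the observed rate is 21/24 = 87.5%. If 5 leave, it is 21/22 = 95.5%. The number leaving is an assumption, and the shift disappears for any failure that was seen and is counted.

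**The case against.** A reader might infer that unblinded investigators will remove the patients most likely to have failed, that their primary readings are lost, and that no analysis could repair this. The documents do not support that.

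- **The six-month reading is requested.** All withdrawn patients are asked to attend the final visit, and the schedule makes six months its natural meaning. A close-out visit on the day of withdrawal is possible only because the term is undefined.
- **A failure that prompts withdrawal has been seen.** A rupture, thrombosis or early loss of patency that leads to withdrawal is already on record. Whether it counts is an analysis decision under 3.9. Only status after withdrawal is lost at collection.
- **Withdrawal is not the stated response to early failure.** Section 3.1 sends a missed stenosis to cross-over and serious complications to admission, and says follow-up may be brought forward. No section names these events as grounds for withdrawal, and no withdrawal rates or reasons are given.
- **Lack of blinding is inferred.** The operator necessarily knows the guidance method, but the documents are silent on blinding.
- **The 12-to-49 range is extreme.** It charges the whole dropout allowance to this rule, assumes six-month status is missing, and sets opposite outcomes in the two arms. It says nothing about the one- and three-month readings.

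All of this stands, and it limits the point. It leaves two facts untouched: no section asks for the interim readings after withdrawal, and the final visit is not defined.

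**Conclusion.** The point holds as a weakness in the withdrawal rule. As written, it permits the one- and three-month primary readings to be lost after a discretionary decision, and that loss may be related to outcome and made with the arm known to the operator. The six-month reading is kept on paper under the natural reading of the final visit.

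The direction and size of any bias are unknown, because the documents give no withdrawal rates or reasons by arm. The range of 12 to 49 points around an observed 37.6 is an outer bound. It rests on 5 of 27 per arm having no six-month status and on the planning rates holding among those seen. The 30.6-point figure, in which all those lost failed, fits better with the worry that failures are the ones lost; there the difference remains significant at 0.05. No figure can be given for the interim time points, since the plan states no expected rates for them.

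This is a cheap improvement worth making before patients are followed. It does not show that the comparison is invalid.

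**What to change.** Rewrite section 3.5 so that:

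1. An investigator's decision to stop or change treatment after the randomised procedure does not end follow-up. Patients who still consent keep the existing two-week, one-, three- and six-month visits.
2. Follow-up ends only when the patient withdraws consent to it. Such patients are asked to allow use of routine dialysis and hospital records to six months, if the consent form does not already cover this (the consent pages were not available for review).
3. The final study visit is defined as the visit six months after the randomised procedure.
4. The date, reason and decision-maker are recorded for each withdrawal and reported by arm.

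The cost is a few sentences in 3.5 and possibly one line in the consent form. In practice it means some visits that are already scheduled and some chart review, for about 10 patients (5 per arm) at the planned dropout. It changes no clinical rule. The per-protocol analysis and the missing-data rule in 3.9 need separate attention: better collection does not settle how the readings are used.
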